The exact sample size for the NCPRR is unknown, and is projected based upon the estimated national figure of adult chronic ITP patients, as well as the anticipated percentage of adult chronic ITP patients who may be treated with romiplostim. Based upon a conservative estimate, the study will have at least 623 adult chronic ITP patients who will receive romiplostim therapy during the study period, which will equate to more than 4,000 patient-years of follow-up. The NHRS of these 3 countries may also be capable of providing records for approximately 1,860 adult chronic ITP patients who are not exposed to romiplostim, which should provide more than 12,700 patient-years of follow-up data.

Summary of Subject Eligibility Criteria

The study population is chronic ITP patients, defined as those who have been diagnosed with ITP for more than 6 months, and who continually receive ITP treatments (eg, ITP medication), and/or have had a splenectomy procedure. Any adult (≥ 18 years) chronic ITP patient who has received at least 1 dose of romiplostim therapy, and who is registered in the NHRS of Denmark, Sweden, and Norway between 01 January 2009 and 31 December 2018, will be eligible subjects for this study. Patients will be continually followed up after discontinuation of romiplostim therapy.

Patients are excluded from the cohorts of chronic ITP patients if either of the following is present:

1. Any diagnosis of another condition associated with thrombocytopenia other than chronic ITP listed in [Appendix 2](#) at any time prior to or within 6 months after the qualifying diagnosis for chronic ITP. Examples of thrombocytopenia associated with other diseases and conditions include systemic lupus erythematosus (SLE), HIV infection, hepatitis C virus infection, malignancy, lymphoproliferative disorders, and myelodysplastic syndrome.
2. Lack of a platelet count below $150 \times 10^9/L$ without obvious cause in the 6 months before or after their first ITP diagnosis code

Comparison Group

Adult chronic ITP patients who are never exposed to romiplostim during the study period will be in the comparison group known as the romiplostim Unexposed Cohort. If patients in the comparison

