1.2 Secondary Objectives

Potential clinical risks:

- To describe the phenomenon of worsened thrombocytopenia (platelet count significantly reduced to, or below, baseline platelet count levels) after romiplostim cessation among adult chronic ITP patients
- To study the incidence rate of thrombocytosis (platelet count $> 450 \times 10^9/L$) among romiplostim-treated adult chronic ITP patients with/without adverse events
- To describe the incidence rate of thrombotic/thromboembolic events and the distribution of specific diagnoses of these thrombotic/thromboembolic events for a romiplostim-exposed cohort and an unexposed cohort
- To assess the incidence rate of hematological malignancies and pre-malignant states (focused on acute myelogenous leukemia [AML] and myelodysplastic syndromes [MDS]) for a romiplostim-exposed cohort and an unexposed cohort
- To describe clinically significant bleeding and/or receipt of rescue medication (any new ITP medication prescribed to a chronic ITP patient during romiplostim therapy) in predefined romiplostim therapy periods ([Section 7.1](#))
- To describe the incidence rate of concurrent leukocytosis and anemia (measured by laboratory test results taken within 4 weeks of each other)

³ Clinical signs: any of the following: splenomegaly, hepatomegaly, leukocytosis, and cytopenia

- To describe patient safety profiles, including the incidence rate of renal failure among adult chronic ITP patients with renal impairment medical condition when romiplostim therapy is initiated
- To measure the impact of the EU dosing rule in the cohort of romiplostim exposed patients

Potential BM abnormal findings:

- To describe the prevalence of reticulin and collagen fiber content in the first BM biopsy of adult chronic ITP patients prior to romiplostim exposure, by splenectomy status
- To assess the incidence of collagen fibrosis with associated clinical signs confirmed by findings in BM biopsies of adults with chronic ITP either receiving or not receiving romiplostim
- To study the incidence of chronic idiopathic myelofibrosis (CIMF, primary myelofibrosis) according to the WHO diagnostic criteria in adults with chronic ITP either receiving or not receiving romiplostim

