3. PATIENT REGISTRY STUDY PLAN

3.1 Registry Design

The NCPRR is established on the basis of the NHRS of 3 Nordic countries: Denmark, Sweden, and Norway.

The study period will be between 01 January 2009 (starting date) and 31 December 2019 (ending date). Interim study reports will be developed for yearly submission to the Agency. Each annual report will describe include events occurring from 01 January through 31 December of the reporting period with cumulative results. All data sources will use the same cutoff date in calendar time, December 31st of the latest year for all data obtained from the NHRS databases. The patient experience (patient time) for all patients who receive at least 1 dose of romiplostim therapy will be included in the romiplostim exposure cohort after they receive romiplostim. The patient experience with ITP time before romiplostim exposure will be included in the romiplostim unexposed cohort, along with that for all adult chronic ITP patients who never receive romiplostim therapy during the study period.

Adult chronic ITP cohorts (romiplostim Exposed Cohort and Unexposed Cohort) include adult patients who are identified as having chronic ITP (incident and prevalent cases through both hospital discharge registry and outpatient clinic registry, as described by [Frederiksen and Schmidt, 1999](#)) on or after the starting date, and up to 1 year prior to the ending date. All patients will be followed-up for **at least 1 year and up to 11 years** in either of 2 cohorts: the romiplostim Exposed Cohort or Unexposed Cohort. Incident and recurrent outcomes of interest will be assessed on an annual basis.

All clinical outcomes (eg, thrombotic/thromboembolic events, hematological malignancies, and other potential outcomes of interest) will be identified by International Classification of Diseases – 10th Revision (ICD-10) codes from the NHRS databases (eg, hospital discharge registry, outpatient clinic registry, pathology registry, death registry, cancer registry, birth registry, and prescription registry) or by review of electronic medical records and/or paper medical charts. As needed, suspected and identified cases will be medically confirmed by review of electronic medical records and/or paper medical charts, laboratory testing results, BM biopsy reports, pathology data, pharmacy data, and other relevant health records. Laboratory data will be used to determine thrombocytosis and worsened thrombocytopenia after cessation of romiplostim.

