3.4 Selection of Participants (or Subject Eligibility)

3.4.1 Inclusion Criteria

Subjects in the NCPRR will be those whose health information is recorded by the NHRS of Denmark, Norway, or Sweden.

The eligible adult cITP romiplostim-exposed patients for the NCPRR must meet all of the following criteria:

- Patients must be 18 years or older at the time of chronic ITP diagnosis,
- Patients will have romiplostim therapy between 01 January 2009 and 31 December 2018, and
- Patients will have at least 6 months of medical information prior to initial date of receiving romiplostim treatment (Index Date), data from which will establish a baseline of study subjects.

The eligible adult cITP romiplostim-unexposed patients for the NCPRR must meet all following criteria:

- Patients must be 18 years or older at the time of chronic ITP diagnosis,
- Patients will not have received romiplostim therapy prior to or during the study period between 01 January 2009 and 31 December 2019, and
- Patients will have at least 6 months of medical information in the study period. The data from this period will establish baseline of subjects in the comparison group.

Eligible romiplostim-unexposed cITP patients will be the source of comparison cohorts for romiplostim-exposed cITP patients. Because potential confounding factors (eg, severity of ITP condition) may cause some biases for the study, however, robust propensity scoring and adjusted analyses will be essential ([Section 12](#)). In addition, appropriate contextualization from other recognized data sources will be used in comparisons to address selection biases.

In addition, according to initial dates of receiving romiplostim therapy among patients in the Exposed Cohort, the follow-up time period will be separated into 2 periods: (1) follow-up time period prior to romiplostim exposure, and (2) follow-up time period following romiplostim exposure. Patient experiences in the follow-up time period prior to the initial date of receiving romiplostim therapy will be considered as another “within-patient” comparison with the patient experiences during the follow-up time period after the initial date of receiving romiplostim therapy.

Eligible romiplostim Off-Label-Exposed patients will be any patient who received romiplostim therapy without an adult chronic ITP diagnosis.

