5.3 Case Ascertainment for BM Abnormality

Cases of BM fibrosis with associated clinical signs will be ascertained using electronic medical record review that will be blinded to romiplostim exposure status. Confirmation of the diagnosis of BM fibrosis will be verified by an evaluation of the results of BM biopsies and clinical presentation.

Reticulin and collagen fiber content information will be gathered from BM biopsies. Since BM biopsies are not routinely obtained when treating ITP patients, an estimate of the incidence rate of reticulin and collagen fiber content from this study would likely be inaccurate. For this reason the prevalence rate of reticulin and collagen fiber content and related grading among patients with BM biopsies stained for reticulin and collagen formation will be calculated. Only data from the first BM biopsy prior to romiplostim therapy will be included in the analysis to reduce bias. This analysis will be conducted by splenectomy status.

Adult chronic ITP patients in both the Exposed Cohort and Unexposed Cohort with both positive findings of reticulin and collagen fiber content and repeated BM biopsies will be

assessed to describe disease progression related to changes in reticulin and collagen fiber content in subsequent BM biopsies.

Incidence of BM abnormal findings (eg, PMF, reticulin, and collagen fiber content formation) will be assessed based upon only patients with BM data prior to and post romiplostim therapy.

The relationship between BM findings of reticulin and collagen fiber content and clinical/laboratory findings will be established using data 6 to 3 months prior to, 3 to 0 months prior to, 0 to 3 months post, and 3 to 6 months post-abnormal BM findings (please see [Section 12.9](#) regarding issues related to missing data).

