6.2 Outcomes

There are many outcomes in the NCPRR. They are:

Primary Outcome Endpoints:

- Incidence of increased BM reticulin and/or BM fibrosis with associated clinical signs⁴, confirmed by findings in BM biopsies among adult chronic ITP patients
- Incidence of reticulin and collagen BM fibrosis (reticulin fibrosis and collagen fibrosis: SNOMED codes: M49000, M49001, M49020, M99611) with associated clinical signs, confirmed by findings in a BM biopsy among adults chronic ITP patients

Secondary Endpoints:

Clinical Endpoints:

- Average platelet counts prior to, during, immediately after treatment cessation, and following romiplostim therapy (study periods are defined in [Section 7.1](#))
- Incidence of thrombocytosis (laboratory confirmation of a platelet count $> 450 \times 10^9/L$) with/without adverse events among adult chronic ITP patients
- Incidence of thrombotic/thromboembolic events (ICD-10: 180, 126)
- Incidence of hematological malignancies (focused on AML and MDS)
- Incidence of clinically significant bleeding and/or receipt of rescue ITP medications for each predefined romiplostim treatment period ([Section 7.1](#))
- Incidence of concurrent leukocytosis and anemia (measured by laboratory test results taken within 4 weeks of each other)
- Description of platelet counts and dose adjustment in mcg/kg of romiplostim in patients with cITP according to dose adjustment rules specified in the European SPC

⁴ Clinical signs: any of the following: splenomegaly, hepatomegaly, leukocytosis, and cytopenia.

BM Endpoints:

- Prevalence of reticulin and collagen fiber content in the first BM biopsies of adult chronic ITP patients prior to romiplostim therapy by splenectomy status
- Incidence of collagen fibrosis with associated clinical signs confirmed by findings in BM biopsies among adult chronic ITP patients
- Incidence of PMF (primary myelofibrosis) (ICD-10: c94.5) according to the WHO diagnostic criteria in adult chronic ITP patients who have BM data prior to and/or post romiplostim therapy
- Overall and specific incidence of BM fibrosis, including reticulin and collagen fiber content formation, and PMF among adult chronic ITP patients with BM data prior to and/or post romiplostim therapy
- Association between the aforementioned primary and secondary clinical outcomes and BM abnormal findings

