12.6 Comparisons of Outcomes that are Dependent on BM Data

1) Frequency and incidence of increased BM reticulin and/or BM fibrosis with associated clinical signs⁵, confirmed by findings in a BM biopsy and 2) frequency and incidence of collagen fibrosis with associated clinical signs confirmed by findings in BM biopsies will be analyzed between the Exposed Cohort and Unexposed Cohort in all adults with chronic ITP:

⁵ Clinical signs: any of the following: splenomegaly, hepatomegaly, leukocytosis, and cytopenia.

- Since the sample size could be very small, the detailed description of each identified case will be listed in the report.
- If there is a sufficient sample size, a formal statistical analytic comparison, as described in [Section 12.4](#), will be conducted.

Description of prevalence rate of reticulin and collagen formation among chronic ITP patients:

- This analysis will be conducted based upon all eligible adult chronic ITP patients in the period prior to romiplostim treatment by splenectomy status. Only initial BM results will be used in the analysis to reduce potential selection bias caused by repeated testing for BM with abnormal findings.
- Prevalence of patients with reticulin and collagen formation in BM will be assessed. No comparison will be conducted; however, the descriptive analysis will be used to describe demographic characteristics, clinical features, and laboratory findings.

1) Frequency and incidence of chronic idiopathic myelofibrosis (primary myelofibrosis) according to the WHO diagnostic criteria, and 2) overall and specific incidence rates of BM fibrosis findings, including reticulin and collagen fiber content formation, and chronic idiopathic myelofibrosis in the Exposed Cohort and Unexposed Cohort in adult chronic ITP patients who have BM data prior to and post romiplostim therapy:

- Since the sample size could be very small for these outcomes, the detailed description of each identified case will be listed in the report.
- If there is a sufficient sample size (e.g., approximately 10 per treatment group for each covariate considered), a formal statistical analytic comparison, as described in [Section 12.4](#), will be conducted.

2) Association of splenomegaly and/or hepatomegaly with BM fibrosis and 2) association of changes in peripheral blood prior to and following the finding of reticulin and collagen fiber content or formation (reticulin grading 1 to 3):

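### For two secondary bone-marrow outcomes, the before-and-after-romiplostim biopsy rule shuts out every never-exposed patient, although incidence is to be reported for both cohorts

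*Protocol*

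**What the plan says.** The PMF objective in Section 1.2 asks for incidence "in adults with chronic ITP either receiving or not receiving romiplostim", with no biopsy condition. The next objective, overall and specific BM fibrosis regardless of signs, covers the same two groups but also asks for marrow data before and following romiplostim.

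The patients who count are then described in three ways:

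- **Both before and after.** Section 5.3 says that incidence of abnormal BM findings, with PMF and fibre formation as examples, "will be assessed based upon only patients with BM data prior to and post romiplostim therapy". The third block of Section 12.6 reports these outcomes "in the Exposed Cohort and Unexposed Cohort in adult chronic ITP patients who have BM data prior to and post romiplostim therapy" and foresees a formal comparison if there are about 10 patients per treatment group for each covariate.
- **Before and/or after.** Section 6.2 words the PMF endpoint as incidence "in adult chronic ITP patients who have BM data prior to and/or post romiplostim therapy". It words the overall fibrosis endpoint the same way, as does the synopsis.
- **At least one stained biopsy.** Section 5.5 bases the biopsy-related secondary endpoints on every ITP patient with at least one registered biopsy stained for reticulin and collagen. It makes no reference to romiplostim.

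The Unexposed Cohort is also described in two ways. The synopsis says "Adult chronic ITP patients who are never exposed to romiplostim during the study period will be in the comparison group", and Section 3.4.1 makes it an eligibility condition: "Patients will not have received romiplostim therapy prior to or during the study period between 01 January 2009 and 31 December 2019". Section 3.1, however, adds pre-treatment time: "The patient experience with ITP time before romiplostim exposure will be included in the romiplostim unexposed cohort".

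**The concern.** A rule that requires marrow data after romiplostim can be met only by someone who has had romiplostim. Applied to both cohorts, it removes the separate comparison group from an analysis meant to report on that group. The half of these two objectives that concerns patients not receiving the drug then cannot be met from the never-exposed patients, even descriptively.

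The competing wordings do not settle the matter, because they give different numerators and denominators. The and/or version can admit unexposed patients. It also admits exposed patients with no marrow examined before treatment, in whom an abnormal finding may predate the drug and should not count as incident. Results go to the regulator every year with cumulative figures, so two annual reports could use different analysis sets and both claim to follow the protocol.

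**Working it through.** **1. The plan's own cohort sizes (Section 3.5).**

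| Step | Prevalent cases | Incident cases |
|---|---|---|
| ITP patients | 570 × 13 = 7,410 | 570 × 10 = 5,700 |
| 20% become chronic | 1,482 | 1,140 |
| 95% remain after attrition | 1,408 | 1,083 |
| 25% exposed | 352 | 271 |
| Remainder unexposed | 1,408 − 352 = 1,056 | 1,083 − 271 = 812 |

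Exposed: 352 + 271 = 623, as stated. Unexposed: 1,056 + 812 = 1,868 against 1,860 stated, a difference of 8 that does not matter here.

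**2. Eligibility set against the analysis set.** The never-exposed are patients without romiplostim before or during the study (Section 3.4.1). The analysis set in Sections 5.3 and 12.6 requires marrow data before romiplostim and after it. For a never-exposed patient the second condition is impossible. With p the share of patients biopsied at both times:

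- never-exposed patients eligible = 1,860 × 0 = 0, for every p;
- exposed patients eligible = 623 × p.

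The protocol gives no biopsy frequency, so p is an assumption shown over a range:

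| Assumed p | Exposed eligible (of 623) | Never-exposed eligible (of 1,860) |
|---|---|---|
| 5% | 31 | 0 |
| 10% | 62 | 0 |
| 20% | 125 | 0 |
| 30% | 187 | 0 |
| 50% | 312 | 0 |

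Never-exposed patients therefore cannot satisfy the condition of about 10 per group per covariate at any biopsy frequency.

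**3. What is left under Section 3.1.** If pre-treatment time counts as unexposed, the comparator is not zero. It then holds only the earlier time of patients who later started romiplostim and were biopsied again after starting. These are the patients in the exposed arm of the same analysis. The synopsis and Section 3.4.1 already describe this before-and-after contrast as another, within-patient comparison.

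**4. Which outcomes the rule reaches.** The first block of Section 12.6 analyses increased reticulin and/or fibrosis with clinical signs, and collagen fibrosis with clinical signs, in all adults with chronic ITP. The restriction appears only in the third block. It reaches PMF and overall/specific fibrosis regardless of signs.

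**The case against.** **Other sections are broader.** Section 5.5 and the and/or wording in Section 6.2 would admit unexposed patients, and Section 5.3 itself plans to follow repeat biopsies in both cohorts. Zero is therefore the result of the narrowest wording. That is true, but the narrowest wording is the one in the analysis section for these outcomes, and Section 5.3 states it with the word 'only'. The broader versions show that the protocol conflicts with itself. They do not show which rule governs.

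**The registry is descriptive.** It tests no hypothesis, comparisons are exploratory, and each identified case is to be described individually. This limits the consequences. It does not remove the problem, because a descriptive rate in unexposed patients also needs patients who can enter its denominator.

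**Stronger readings that the protocol does not support.**

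- A reader might infer that all BM incidence, including the primary endpoint, has lost its comparator. It has not. The primary endpoint is analysed in all adults with chronic ITP, and the primary objective concerns treated patients only.
- A reader might infer that the comparator is wholly empty. Section 3.1 leaves the pre-treatment time of later-treated patients in it.
- A reader might put a size on under-ascertainment or on a biopsy-driven rate ratio, starting from the remark in Section 5.3: "Since BM biopsies are not routinely obtained when treating ITP patients". The protocol gives no biopsy frequency by cohort. It lists increased reticulin among the identified and potential risks but does not say that this changes biopsy practice. Clinical signs may themselves prompt a biopsy. Unequal ascertainment is a reason to report biopsy counts and cannot be quantified from this document.

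**Conclusion.** The point holds for two secondary outcomes: PMF, and overall/specific BM fibrosis regardless of clinical signs. As Sections 5.3 and 12.6 are written, none of the planned 1,860 never-exposed patients can enter either analysis. This follows from the definitions and rests on no assumption about biopsy rates. The remaining unexposed time is a within-patient contrast, selected on later treatment and later biopsy, and it does not stand in for a separate cohort. The wording also conflicts with Sections 5.5 and 6.2 and, for PMF, with the unrestricted objective in Section 1.2. The primary result is untouched. The rule is nevertheless wrong as written and should be corrected before these rates are reported by cohort.

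**What to change.** Use one analysis set, defined so that both cohorts can meet it, in the synopsis endpoints and in Sections 1.2, 5.3, 5.5, 6.2 and 12.6:

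- **Baseline:** an evaluable biopsy without the finding. For exposed patients this is before first romiplostim. For unexposed patients, including pre-exposure time, it is the first evaluable biopsy at or after the ITP work-up. It should not have to precede the Index Date, because Section 4.1 sets that date at diagnosis for unexposed patients diagnosed from 01 April 2009. Such a condition would exclude diagnostic biopsies taken afterwards.
- **Follow-up:** at least one later evaluable biopsy.
- **Person-time:** counted from the later of the baseline biopsy and cohort entry.
- **Exposed cases without baseline marrow:** listed separately, outside the incidence rate.
- **Beside each BM rate:** the number of patients biopsied and biopsies per 100 patient-years, by cohort, since biopsies are not routine and ascertainment may differ.

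The cost is wording and some table columns, drawn from pathology-registry data that Section 5.5 already relies on. No new biopsies are needed. Numbers will be smaller than under the and/or wording. Eligibility will still depend on having a repeat biopsy, which is itself a selection and should be stated as a limitation.

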- Association of changes in peripheral blood with listed BM abnormal findings (3 to 6 months prior to, 0 to 3 months prior to, 0 to 3 months post, and 3 to 6 months post-abnormal BM findings)

Romiplostim Off-label Use

- Romiplostim utilization in patients without adult chronic ITP assessed by underlying disease for which the drug is used.

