- The association tests will be based on data 3 to 6 months prior to, 0 to 3 months prior to, 0 to 3 months post, and 3 to 6 months post-positive findings in BM biopsies.
- 2XN tabulation will be created and chi-square tests for categorical variables will be used to test the association.
- Multiple regression and logistic analysis will be used to investigate romiplostim's effect after adjusting for other confounders, if feasible.

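### Section 12.6 asks about blood changes before and after a positive marrow finding, but names only a chi-square on an undefined 2xN table; if the time windows are the columns, a paired or clustered method is needed.

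*Protocol*

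**What the plan says.** Section 6.2 lists a secondary bone marrow endpoint: "Association of changes in peripheral blood with listed BM abnormal findings". Section 12.6 gives its analysis and puts two questions under one set of bullets. One is "Association of splenomegaly and/or hepatomegaly with BM fibrosis". The other is "association of changes in peripheral blood prior to and following the finding of reticulin and collagen fiber content or formation", with reticulin grades 1 to 3 in scope.

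Three bullets follow:

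- The data: "The association tests will be based on data 3 to 6 months prior to, 0 to 3 months prior to, 0 to 3 months post", plus a fourth window, "3 to 6 months post-positive findings in BM biopsies". There are thus two windows before and two after, all anchored on a positive biopsy.
- The test: "2XN tabulation will be created and chi-square tests for categorical variables will be used to test the association".
- A regression step: "Multiple regression and logistic analysis will be used to investigate romiplostim's effect after adjusting for other confounders, if feasible".

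The section does not say what the two rows and N columns are. It names no paired or repeated-measures method for these questions.

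**The concern.** A before-and-after question about blood counts around one biopsy is a within-patient contrast. The windows exist only for patients with a positive biopsy, and the analysis names no negative-biopsy comparator. A natural table is therefore abnormal yes/no by window. In that table one patient can supply an entry to each of up to four columns, whereas Pearson's chi-square treats the columns as independent groups of different people.

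Blood counts in one patient a few months apart will usually be positively correlated. The chi-square then overstates the variance of differences between windows and rejects too rarely. In a registry meant for signal detection that is the unhelpful direction: a real change around a reticulin or collagen finding could be reported as no association. The regression bullet does not cover this. It addresses the effect of romiplostim, applies only if feasible, and mentions no within-patient correlation.

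**Working it through.** **Inputs from the protocol.** Four windows, a chi-square test and a 2xN table (Section 12.6). The protocol gives no sample size, significance level, abnormality rate or correlation for this test, so there is no figure of its own to reproduce.

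**Assumed inputs.** The windows are the columns; the same n patients have data in all four; n = 20, 40 or 80; nominal level 5%. The null case has 30% abnormal in every window. The change case has 20%, 20%, 40% and 40%. Within-patient correlation ρ between the binary results is 0, 0.3, 0.5 or 0.7, equal for every pair of windows and calibrated at the 30% rate.

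**Analytic check of the null.** Let c_j be the number abnormal in window j. For equally correlated windows with common rate p, contrasts among the c_j have variance proportional to n·p(1−p)(1−ρ). Pearson's statistic scales by n·p(1−p) alone. In large samples it is therefore distributed as (1−ρ) times a chi-square on 3 degrees of freedom, and the true rejection rate is P(χ²₃ > 7.815/(1−ρ)):

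- ρ = 0: 7.815/1.0 = 7.815, giving 0.050
- ρ = 0.3: 7.815/0.7 = 11.16, giving 0.0109
- ρ = 0.5: 7.815/0.5 = 15.63, giving 0.0014
- ρ = 0.7: 7.815/0.3 = 26.05, giving less than 0.0001

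**Simulation.** Correlated binary results came from a latent normal, with 20,000 replicates per setting. Pearson's chi-square on the 2x4 table was compared with Cochran's Q on the same data.

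| n | ρ | Null: chi-square | Null: Q | Power: chi-square | Power: Q |
|---|---|---|---|---|---|
| 20 | 0 | 0.054 | 0.048 | 0.34 | 0.32 |
| 20 | 0.3 | 0.012 | 0.044 | 0.27 | 0.43 |
| 20 | 0.5 | 0.003 | 0.040 | 0.22 | 0.56 |
| 20 | 0.7 | <0.001 | 0.027 | 0.18 | 0.71 |
| 40 | 0 | 0.049 | 0.047 | 0.63 | 0.62 |
| 40 | 0.3 | 0.012 | 0.048 | 0.61 | 0.79 |
| 40 | 0.5 | 0.001 | 0.046 | 0.58 | 0.91 |
| 40 | 0.7 | <0.001 | 0.041 | 0.54 | 0.98 |
| 80 | 0 | 0.049 | 0.049 | 0.93 | 0.93 |
| 80 | 0.3 | 0.012 | 0.049 | 0.95 | 0.985 |
| 80 | 0.5 | 0.001 | 0.049 | 0.957 | 0.998 |
| 80 | 0.7 | <0.001 | 0.048 | 0.96 | 1.00 |

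At ρ = 0.5 the loss is 56 − 22 = 34 points with 20 patients, 91 − 58 = 33 points with 40, and about 4 points with 80. At ρ = 0 there is none.

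**A second pattern of change.** With rates of 20%, 30%, 40% and 45%, 30 patients and a latent correlation of 0.5 (about 0.3 on the binary scale), power is 37% for chi-square and about 60% for Q. At a latent correlation of 0.7 it is 32% against 71%. Direction and order of size agree with the table.

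**Control case: one entry per patient.** Blood abnormality by three reticulin grades within a single window was simulated with 5,000 replicates. Chi-square rejected 0.049, 0.052 and 0.051 of the time at n = 20, 40 and 80. It is valid there, so the fault depends on the layout of the table.

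**The case against.** The strongest reply is that the protocol never says the windows are the columns. It names them as the source of the data, and the phrase on reticulin grades 1 to 3 just above offers a natural N. Read that way, the table is blood abnormality, or change category, by marrow grade with one entry per patient, and chi-square is sound. The same holds for organomegaly by fibrosis under the same bullets. This stands, and it makes the point conditional. It does not remove it, because on that layout no test is named for the direct before-and-after comparison of windows.

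A reader might infer that the same patients fill every window. The documents do not say so. Section 5.1 skips chart review for a reporting period without hospital contact, and Section 5.3 refers to Section 12.9 on missing data for these very windows. Some overlap of patients across windows is enough for the concern, but complete windows are an assumption of the simulation.

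A reader might also take the warnings in Section 12.6 about very small samples to cover this analysis. They belong to other blocks of that section. That numbers are limited here is an inference from Section 5.3, which says biopsies are not routine in ITP.

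Nor do the documents support saying that real changes will be missed. That depends on the layout, on positive correlation and on small numbers. The study calls itself descriptive and hypothesis generating, the endpoint is secondary, and fibrosis cases are also described in narratives.

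Lastly, table layout is often left to a statistical analysis plan. That is fair for the layout alone. Here, however, the protocol itself names the test, and the test does not suit one plausible reading of its own question.

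**Conclusion.** The point holds conditionally. Section 12.6 poses a before-and-after question over four windows, names a test for independent groups, and leaves the table undefined. If windows are compared, Pearson's chi-square has the wrong null distribution. With binary correlation from 0.3 to 0.7, a nominal 5% test rejects about 1.2% of the time or less, and with 20 to 40 patients it gives up roughly 16 to 53 points of power against Cochran's Q under the 20/20/40/40% pattern (79 − 61 = 18 to 98 − 54 = 44 points at n = 40; 43 − 27 = 16 to 71 − 18 = 53 at n = 20). The loss is small at 80 patients and nil at zero correlation. Rates, correlations, patient numbers and complete windows are all assumptions. If each patient appears once in the table, the chi-square is valid. Because the analysis is secondary and exploratory, with no decision rule attached, this is a minor-to-moderate correction.

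**What to change.** In Section 12.6:

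- State the rows and columns of each 2xN table, separately for the organomegaly question and the peripheral blood question.
- Where windows are compared within patients, replace the chi-square with exact McNemar (before against after) or Cochran's Q over the four windows. At the smallest numbers an exact or permutation form of Q is preferable.
- Where some patients lack a window, use GEE logistic regression clustered on patient.
- Keep chi-square or Fisher's exact test only for tables in which each patient appears once, such as organomegaly by marrow fibrosis, or blood abnormality by reticulin grade within one window.

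The cost is a sentence or two of text. No new data are needed.
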